14.3.1.1 Solicited Adverse Events

There are no solicited AEs.

14.3.1.2 Unsolicited Adverse Events

Table 12: Summary of Unsolicited Adverse Events by MedDRA System Organ Class, Higher Level Group Term, and Preferred Term

MedDRA System Organ Class	MedDRA Higher Level Group Term	MedDRA Preferred Term	Any Time Post Dose (N=X)			
			n	%	95% CI	Events
Any SOC	Any HLGT	Any PT	x	xx	xx, xx	X
[SOC 1]	HLGT 1	[PT 1]				
		[PT 2]				
[SOC 2]	HLGT 2	[PT 1]				
		[PT 2]				

Table 13: Unsolicited Adverse Events by MedDRA System Organ Class, Higher Level Group Term, Preferred Term, Maximum Severity, and Relationship

MedDRA System Organ Class	MedDRA Higher Level Group Term	Preferred Term	Severity	All Subjects (N = X)			
				Related		Any Relatedness	
				n	%	n	%
Any SOC	Any HLGT	Any PT	Any Severity	x	x	x	x
			Mild	x	x	x	x
			Moderate	x	x	x	x
			Severe	x	x	x	x
SOC 1	Any HLGT	Any PT	Any Severity	x	x	x	x
			Mild	x	x	x	x
			Moderate	x	x	x	x
			Severe	x	x	x	x
SOC 2	HLGT 1	Any PT	Any Severity	x	x	x	x
			Mild	x	x	x	x
			Moderate	x	x	x	x
			Severe	x	x	x	x
SOC 3	HLGT 1	PT 1	Any Severity	x	x	x	x
			Mild	x	x	x	x
			Moderate	x	x	x	x
			Severe	x	x	x	x

Note: N = Number of subjects in the Safety Analysis Population.

[1] For severity, a subject is counted once per preferred term and is summarized according to their highest severity. Events are summarized separately for related events only and all AEs regardless of relatedness.

14.3.2 Listing of Deaths, Other Serious and Significant Adverse Events

Table 14: Listing of Serious Adverse Events

AE	No. of Days Post Associated Dose (Duration)	No. of Days Post Dose the Event Became Serious	Reason Reported as an SAE	Severity	Relationship to Study Treatment	If Not Related, Alternative Etiology	Action Taken with Study Treatment	Subject Discontinued Due to AE	Outcome	MedDRA System Organ Class	MedDRA Higher Level Group Term	MedDRA Preferred Term
Subject ID:, AE Number:												
Comments:												
Subject ID:, AE Number:												
Comments:												

Table 15: Listing of Non-Serious, Unsolicited, Moderate or Severe Adverse Events

AE	No. of Days Post Associated Dose (Duration)	No. of Days Post Dose the Event Became Serious	Reason Reported as an SAE	Severity	Relationship to Study Treatment	If Not Related, Alternative Etiology	Action Taken with Study Treatment	Subject Discontinued Due to AE	Outcome	MedDRA System Organ Class	MedDRA Higher Level Group Term	MedDRA Preferred Term
Subject ID:, AE Number:												
Comments:												
Subject ID:, AE Number:												
Comments:												

14.3.3 Narratives of Deaths, Other Serious and Significant Adverse Events

This is a placeholder for the CSR.

14.3.4 Abnormal Laboratory Value Listings (by Subject)

Table 16: Listing of Abnormal Laboratory Results - Chemistry

Subject ID	Sex	Age (years)	Fasting Status	Planned Time Point	Actual Study Day	Laboratory Parameter (Units)	Result (Severity)	Relationship to Treatment	If Not Related, Alternate Etiology	Clinically Significant?

Table 17: Listing of Abnormal Laboratory Results - Hematology

Subject ID	Sex	Age (years)	Planned Time Point	Actual Study Day	Laboratory Parameter (Units)	Result (Severity)	Relationship to Treatment	If Not Related, Alternate Etiology	Clinically Significant?

Table 18: Listing of Abnormal Laboratory Results - Urinalysis

Subject ID	Sex	Age (years)	Planned Time Point	Actual Study Day	Laboratory Parameter (Units)	Result (Severity)	Relationship to Treatment	If Not Related, Alternate Etiology	Clinically Significant?

14.3.5 Displays of Laboratory Results

14.3.5.1 Chemistry Results

Table 19: Chemistry Laboratory Results by Severity and Time Point – Any Chemistry Parameter

		None		Mild/ Grade 1		Moderate/ Grade 2		Severe/ Grade 3		Missing	
Time Point	N	n	%	N	%	n	%	N	%	n	%
Baseline	x	x	x	X	X	x	x	X	x	x	X
Day 4	x	x	x	X	X	x	x	X	x	x	X
Max Severity Post Baseline	x	x	x	X	X	x	x	X	x	x	X

Note: The “Max Severity Post Baseline” rows indicate the maximum severity experienced by each subject at any time point post baseline, including unscheduled assessments. N=Number of subjects in the Safety Population.

Table 20: Chemistry Laboratory Results by Severity and Time Point – Sodium

Time Point	N	None		Mild/ Grade 1 (Low)		Mild/ Grade 1 (High)		Moderate/ Grade 2 (Low)		Moderate/ Grade 2 (High)		Severe/ Grade 3 (Low)		Severe/ Grade 3 (High)		Missing	
		n	%	n	%	N	%	n	%	n	%	n	%	N	%	n	%
Baseline	x	x	x	x	x	X	x	x	x	x	x	x	x	X	x	x	x
Day 4	x	x	x	x	x	X	x	x	x	x	x	x	x	x	x	x	x
Max Severity Post Baseline	x	x	x	x	x	X	x	x	x	x	x	x	x	x	x	x	x

Note: The “Max Severity Post Baseline” rows indicate the maximum severity experienced by each subject at any time point post baseline, including unscheduled assessments. N=Number of subjects in the Safety Population.

Table 21: Chemistry Laboratory Results by Severity and Time Point – Potassium

This table will repeat Table 20 for Potassium.

Table 22: Chemistry Laboratory Results by Severity and Time Point – Bicarbonate

This table will repeat Table 20 for Bicarbonate.

Table 23: Chemistry Laboratory Results by Severity and Time Point – Glucose

This table will repeat Table 20 for Glucose.

Table 24: Chemistry Laboratory Results by Severity and Time Point – Blood Urea Nitrogen

This table will repeat Table 19 for Blood Urea Nitrogen.

Table 25: Chemistry Laboratory Results by Severity and Time Point – Creatinine

This table will repeat Table 19 for Creatinine.

Table 26: Chemistry Laboratory Results by Severity and Time Point – Protein

This table will repeat Table 19 for Protein.

Table 27: Chemistry Laboratory Results by Severity and Time Point – Albumin

This table will repeat Table 19 for Albumin.

Table 28: Chemistry Laboratory Results by Severity and Time Point – Aspartate Aminotransferase

This table will repeat Table 19 for Aspartate Aminotransferase.

Table 29: Chemistry Laboratory Results by Severity and Time Point – Alanine Aminotransferase

This table will repeat Table 20 for Alanine Aminotransferase.

Table 30: Chemistry Laboratory Results by Severity and Time Point – Alkaline Phosphatase

This table will repeat Table 19 for Alkaline Phosphatase.

Table 31: Chemistry Laboratory Results by Severity and Time Point – Bilirubin

This table will repeat Table 19 for Bilirubin.
--

Table 32 Chemistry Abnormal Laboratory Results Related to Study Treatment by Severity and Time Point – Any Chemistry Parameter

Time Point	N	Mild/ Grade 1		Moderate/ Grade 2		Severe/ Grade 3	
		n	%	n	%	N	%
Baseline	x	x	x	x	x	X	x
Day 4	x	x	x	x	x	X	x
Max Severity Post Baseline	x	x	x	x	x	X	x

Note: The “Max Severity Post Baseline” rows indicate the maximum severity experienced by each subject at any time point post baseline, including unscheduled assessments. N=Number of subjects in the Safety Population.

Table 33: Chemistry Abnormal Laboratory Results Related to Study Treatment by Severity and Time Point – Sodium

Time Point	N	Mild/ Grade 1 (Low)		Mild/ Grade 1 (High)		Moderate/ Grade 2 (Low)		Moderate/ Grade 2 (High)		Severe/ Grade 3 (Low)		Severe/ Grade 3 (High)	
		n	%	n	%	n	%	n	%	n	%	n	%
Baseline	x	x	x	x	x	x	x	x	x	x	x	x	x
Day 4	x	x	x	x	x	x	x	x	x	x	x	x	x
Max Severity Post Baseline	x	x	x	x	x	x	x	x	x	x	x	x	x

Note: The “Max Severity Post Baseline” rows indicate the maximum severity experienced by each subject at any time point post baseline, including unscheduled assessments. N=Number of subjects in the Safety Population.

Table 34: Chemistry Abnormal Laboratory Results Related to Study Treatment by Severity and Time Point – Potassium

This table will repeat Table 33 for Potassium.

Table 35: Chemistry Abnormal Laboratory Results Related to Study Treatment by Severity and Time Point – Bicarbonate

This table will repeat Table 33 for Bicarbonate.

Table 36: Chemistry Abnormal Laboratory Results Related to Study Treatment by Severity and Time Point – Glucose

This table will repeat Table 33 for Glucose.

Table 37: Chemistry Abnormal Laboratory Results Related to Study Treatment by Severity and Time Point – Blood Urea Nitrogen

This table will repeat Table 32 for Blood Urea Nitrogen.

Table 38: Chemistry Abnormal Laboratory Results Related to Study Treatment by Severity and Time Point – Creatinine

This table will repeat Table 32 for Creatinine.

Table 39: Chemistry Abnormal Laboratory Results Related to Study Treatment by Severity and Time Point – Protein

This table will repeat Table 32 for Protein.

Table 40: Chemistry Abnormal Laboratory Results Related to Study Treatment by Severity and Time Point – Albumin

This table will repeat Table 32 for Albumin.

Table 41: Chemistry Abnormal Laboratory Results Related to Study Treatment by Severity and Time Point – Aspartate Aminotransferase

This table will repeat Table 32 for Aspartate Aminotransferase.

Table 42: Chemistry Abnormal Laboratory Results Related to Study Treatment by Severity and Time Point – Alanine Aminotransferase

This table will repeat Table 32 for Alanine Aminotransferase.

Table 43: Chemistry Abnormal Laboratory Results Related to Study Treatment by Severity and Time Point – Alkaline Phosphatase

This table will repeat Table 32 for Alkaline Phosphatase.

Table 44: Chemistry Abnormal Laboratory Results Related to Study Treatment by Severity and Time Point – Bilirubin

This table will repeat Table 32 for Bilirubin.

Table 45: Chemistry Laboratory Summary Statistics by Time Point – Sodium (mmol/L)

Time Point	N	Mean	Standard Deviation	Median	Min, Max
Baseline	x	x.x	x.x	x.x	x, x
Day 4	x	x.x	x.x	x.x	x, x
Day 4, Change from Baseline	x	x.x	x.x	x.x	x, x

Note: N=Number of subjects in the Safety Population with the laboratory result assessed at the respective time point.

Table 46: Chemistry Laboratory Summary Statistics by Time Point – Potassium (mmol/L)

This table will repeat Table 45 for Potassium.

Table 47: Chemistry Laboratory Summary Statistics by Time Point – Magnesium (mg/dL)

This table will repeat Table 45 for Magnesium.

Table 48: Chemistry Laboratory Summary Statistics by Time Point – Chloride (mmol/L)

This table will repeat Table 45 for Chloride.

Table 49: Chemistry Laboratory Summary Statistics by Time Point – Bicarbonate (mmol/L)

This table will repeat Table 45 for Bicarbonate.

Table 50: Chemistry Laboratory Summary Statistics by Time Point – Glucose (mg/dL)

This table will repeat Table 45 for Glucose.

Table 51: Chemistry Laboratory Summary Statistics by Time Point – Blood Urea Nitrogen (mg/dL)

This table will repeat Table 45 for Blood Urea Nitrogen.

Table 52: Chemistry Laboratory Summary Statistics by Time Point – Creatinine (mg/dL)

This table will repeat Table 45 for Creatinine.

Table 53: Chemistry Laboratory Summary Statistics by Time Point – Protein (g/dL)

This table will repeat Table 45 for Protein.

Table 54: Chemistry Laboratory Summary Statistics by Time Point – Albumin (g/dL)

This table will repeat Table 45 for Albumin.

Table 55: Chemistry Laboratory Summary Statistics by Time Point – Aspartate Aminotransferase (U/L)

This table will repeat Table 45 for Aspartate Aminotransferase.

Table 56: Chemistry Laboratory Summary Statistics by Time Point – Alanine Aminotransferase (U/L)

This table will repeat Table 45 for Alanine Aminotransferase.

Table 57: Chemistry Laboratory Summary Statistics by Time Point – Alkaline Phosphatase (U/L)

This table will repeat Table 45 for Alkaline Phosphatase.

Table 58: Chemistry Laboratory Summary Statistics by Time Point – Bilirubin (mg/dL)

This table will repeat Table 45 for Bilirubin.

Table 59: Chemistry Laboratory Summary Statistics by Time Point – Direct Bilirubin (mg/dL)

This table will repeat Table 45 for Direct Bilirubin.

Table 60: Hematology Laboratory Results by Severity and Time Point – Any Hematology Parameter

This table will repeat Table 19 for Any Hematology Parameter.

Table 61: Hematology Laboratory Results by Severity and Time Point – Hemoglobin

This table will repeat Table 19 for Hemoglobin.

Table 62: Hematology Laboratory Results by Severity and Time Point – Leukocytes

This table will repeat Table 19 for Leukocytes.

Table 63: Hematology Laboratory Results by Severity and Time Point – Neutrophils

This table will repeat Table 19 for Neutrophils.

Table 64: Hematology Laboratory Results by Severity and Time Point – Lymphocytes

This table will repeat Table 19 for Lymphocytes.

Table 65: Hematology Laboratory Results by Severity and Time Point – Monocytes

This table will repeat Table 19 for Monocytes.

Table 66: Hematology Laboratory Results by Severity and Time Point – Eosinophils

This table will repeat Table 19 for Eosinophils.

Table 67: Hematology Laboratory Results by Severity and Time Point – Basophils

This table will repeat Table 19 for Basophils.

Table 68: Hematology Laboratory Results by Severity and Time Point – Platelets

This table will repeat Table 19 for Platelets.

Table 69: Hematology Abnormal Laboratory Results Related to Study Treatment by Severity and Time Point – Any Hematology Parameter

This table will repeat Table 32 for Any Hematology Parameter.

Table 70: Hematology Abnormal Laboratory Results Related to Study Treatment by Severity and Time Point – Hemoglobin

This table will repeat Table 32 for Hemoglobin.

Table 71: Hematology Abnormal Laboratory Results Related to Study Treatment by Severity and Time Point – Leukocytes

This table will repeat Table 32 for Leukocytes.

Table 72: Hematology Abnormal Laboratory Results Related to Study Treatment by Severity and Time Point – Neutrophils

This table will repeat Table 32 for Neutrophils.

Table 73: Hematology Abnormal Laboratory Results Related to Study Treatment by Severity and Time Point – Lymphocytes

This table will repeat Table 32 for Lymphocytes.

Table 74: Hematology Abnormal Laboratory Results Related to Study Treatment by Severity and Time Point – Monocytes

This table will repeat Table 32 for Monocytes.

Table 75: Hematology Abnormal Laboratory Results Related to Study Treatment by Severity and Time Point – Eosinophils

This table will repeat Table 32 for Eosinophils.

Table 76: Hematology Abnormal Laboratory Results Related to Study Treatment by Severity and Time Point – Basophils

This table will repeat Table 32 for Basophils.

Table 77: Hematology Abnormal Laboratory Results Related to Study Treatment by Severity and Time Point – Platelets

This table will repeat Table 32 for Platelets.

Table 78: Hematology Laboratory Summary Statistics by Time Point – Hemoglobin (g/dL)

This table will repeat Table 45 for Hemoglobin.

Table 79: Hematology Laboratory Summary Statistics by Time Point – Hematocrit (%)

This table will repeat Table 45 for Hematocrit.

Table 80: Hematology Laboratory Summary Statistics by Time Point – Erythrocytes ($10^{12}/L$)

This table will repeat Table 45 for Erythrocytes.

Table 81: Hematology Laboratory Summary Statistics by Time Point – Leukocytes ($10^9/L$)

This table will repeat Table 45 for Leukocytes.

Table 82: Hematology Laboratory Summary Statistics by Time Point – Neutrophils ($10^9/L$)

This table will repeat Table 45 for Neutrophils.

Table 83: Hematology Laboratory Summary Statistics by Time Point – Lymphocytes ($10^9/L$)

This table will repeat Table 45 for Lymphocytes.

Table 84: Hematology Laboratory Summary Statistics by Time Point – Monocytes ($10^9/L$)

This table will repeat Table 45 for Monocytes.

Table 85: Hematology Laboratory Summary Statistics by Time Point – Eosinophils ($10^9/L$)

This table will repeat Table 45 for Eosinophils.

Table 86: Hematology Laboratory Summary Statistics by Time Point – Basophils ($10^9/L$)

This table will repeat Table 45 for Basophils.

Table 87: Hematology Laboratory Summary Statistics by Time Point – Platelets ($10^9/L$)

This table will repeat Table 45 for Platelets.

Table 88: Urinalysis Laboratory Results by Severity and Time Point – Any Urinalysis Parameter

This table will repeat Table 19 for Any Urinalysis Parameter.

Table 89: Urinalysis Laboratory Results by Severity and Time Point – Protein

This table will repeat Table 19 for Protein.

Table 90: Urinalysis Laboratory Results by Severity and Time Point – Glucose

This table will repeat Table 19 for Glucose.

Table 91: Urinalysis Laboratory Results by Severity and Time Point – Hemoglobin

This table will repeat Table 19 for Hemoglobin.

Table 92: Urinalysis Abnormal Laboratory Results Related to Study Treatment by Severity and Time Point – Any Urinalysis Parameter

This table will repeat Table 32 for Any Urinalysis Parameter.

Table 93: Urinalysis Abnormal Laboratory Results Related to Study Treatment by Severity and Time Point – Protein

This table will repeat Table 32 for Protein.

Table 94: Urinalysis Abnormal Laboratory Results Related to Study Treatment by Severity and Time Point – Glucose

This table will repeat Table 32 for Glucose.

Table 95: Urinalysis Abnormal Laboratory Results Related to Study Treatment by Severity and Time Point – Hemoglobin

This table will repeat Table 32 for Hemoglobin.

14.3.6 Displays of Vital Signs**Table 96: Vital Signs by Assessment, Maximum Severity, and Time Point – Any Assessment**

This table will repeat Table 19 for Vital Signs – Any Assessment.

Table 97: Vital Signs by Assessment, Maximum Severity, and Time Point – Systolic Blood Pressure

This table will repeat Table 20 for Vital Signs – Systolic Blood Pressure.

Table 98: Vital Signs by Assessment, Maximum Severity, and Time Point – Diastolic Blood Pressure

This table will repeat Table 19 for Vital Signs – Diastolic Blood Pressure.

Table 99: Vital Signs by Assessment, Maximum Severity, and Time Point – Pulse Rate

This table will repeat Table 20 for Vital Signs – Pulse Rate.

Table 100: Vital Signs by Assessment, Maximum Severity, and Time Point – Respiratory Rate

This table will repeat Table 19 for Vital Signs – Respiratory Rate.

Table 101: Vital Signs by Assessment, Maximum Severity, and Time Point –Temperature

This table will repeat Table 19 for Vital Signs – Temperature.

Table 102: Vital Signs Summary Statistics by Assessment and Time Point – Systolic Blood Pressure (mmHg)

Time Point	N	Mean	Standard Deviation	Median	Min, Max
Baseline					
1 h (± 10 min) after dosing					
1 h, Change from Baseline					
2 h (± 10 min) after dosing					
2 h, Change from Baseline					
4 h (± 10 min) after dosing					
4 h, Change from Baseline					
Day 2					
Day 2, Change from Baseline					
Day 3					
Day 3, Change from Baseline					
Day 4					
Day 4, Change from Baseline					
Day 8					
Day 8, Change from Baseline					

N = number of subjects in the Safety Population with the vital sign assessed for the respective time point

Table 103: Vital Signs Summary Statistics by Assessment and Time Point – Diastolic Blood Pressure (mmHg)

This table will repeat Table 102 for Diastolic Blood Pressure.

Table 104: Vital Signs Summary Statistics by Assessment and Time Point – Pulse Rate (beats/min)

This table will repeat Table 102 for Pulse Rate.

Table 105: Vital Signs Summary Statistics by Assessment and Time Point – Respiratory Rate (breaths/min)

This table will repeat Table 102 for Respiratory Rate.

Table 106: Vital Signs Summary Statistics by Assessment and Time Point –Temperature (C)

This table will repeat Table 102 for Temperature.

14.3.7 Displays of ECG Measurements**Table 107: ECG Overall Interpretations, Post Dose Compared to Baseline**

ECG Interpretation	n (%)
1 Hours (± 10 min) After Dosing (N=X)	
Normal at Both Times	x (x)
Normal to Abnormal, NCS	x (x)
Normal to Abnormal, CS	x (x)
Abnormal, NCS at Both Times	x (x)
Abnormal, NCS to Abnormal, CS	x (x)
Abnormal, NCS to Normal	x (x)
2 Hours (± 10 min) After Dosing (N=X)	
Normal at Both Times	x (x)
Normal to Abnormal, NCS	x (x)
Normal to Abnormal, CS	x (x)
Abnormal, NCS at Both Times	x (x)
Abnormal, NCS to Abnormal, CS	x (x)
Abnormal, NCS to Normal	x (x)
4 Hours (± 10 min) After Dosing (N=X)	
Normal at Both Times	x (x)
Normal to Abnormal, NCS	x (x)
Normal to Abnormal, CS	x (x)
Abnormal, NCS at Both Times	x (x)
Abnormal, NCS to Abnormal, CS	x (x)
Abnormal, NCS to Normal	x (x)
72 Hours (± 2 hours) After Dosing (N=X)	
Normal at Both Times	x (x)
Normal to Abnormal, NCS	x (x)
Normal to Abnormal, CS	x (x)
Abnormal, NCS at Both Times	x (x)
Abnormal, NCS to Abnormal, CS	x (x)
Abnormal, NCS to Normal	x (x)

Note: N = number of subjects in safety population with the ECG measurement at the visit indicated above the table. CS = clinically significant; NCS = not clinically significant.

Table 108: ECG by Parameter, Maximum Severity, and Time Point – PR Interval, Aggregate

		None		Mild/ Grade 1		Moderate/ Grade 2		Severe/ Grade 3		Missing	
Time Point	N	n	%	n	%	n	%	n	%	n	%
Baseline	x	x	x	x	x	x	x	x	x	x	x
1 hr Post-Dose	x	x	x	x	x	x	x	x	x	x	x
2 hr Post-Dose	x	x	x	x	x	x	x	x	x	x	x
4 hr Post-Dose	x	x	x	x	x	x	x	x	x	x	x
72 hr Post-Dose	x	x	x	x	x	x	x	x	x	x	x
Max Severity Post Baseline	x	x	x	x	x	x	x	x	x	x	x

Note: The “Max Severity Post Baseline” rows indicate the maximum severity experienced by each subject at any time point post baseline, including unscheduled assessments. N=Number of subjects in the Safety Population.

Table 109: ECG by Parameter, Maximum Severity, and Time Point – QTcF Interval, Aggregate

This table will repeat Table 108 for QTcF Interval, Aggregate.
--

Table 110: ECG Summary Statistics by Parameter and Time Point – PR Interval, Aggregate (msec)

Time Point	N	Mean	Standard Deviation	Median	Min, Max
Baseline					
1 h (± 10 min) after dosing					
1 h, Change from Baseline					
2 h (± 10 min) after dosing					
2 h, Change from Baseline					
4 h (± 10 min) after dosing					
4 h, Change from Baseline					
72 h (± 2 h) after dosing					
72 h, Change from Baseline					

N = number of subjects in the Safety Population with the ECG parameter assessed for the respective time point

Table 111: ECG Summary Statistics by Parameter and Time Point – QRS Duration, Aggregate (msec)

This table will repeat Table 110 for QRS Duration, Aggregate.

Table 112: ECG Summary Statistics by Parameter and Time Point – QT Interval, Aggregate (msec)

This table will repeat Table 110 for QT Interval, Aggregate.

Table 113: ECG Summary Statistics by Parameter and Time Point – QTcF Interval, Aggregate (msec)

This table will repeat Table 110 for QTcF Interval, Aggregate.

Table 114: ECG Summary Statistics by Parameter and Time Point – RR Interval, Aggregate (msec)

This table will repeat Table 110 for RR Interval, Aggregate.

Table 115: ECG Summary Statistics by Parameter and Time Point – ECG Mean Ventricular Rate (msec)

This table will repeat Table 110 for ECG Mean Ventricular Rate.

Table 116: ECG Measurements, Frequency of QTcF Prolongation

Time Point	Prolongation Between 30 and <60 msec		Prolongation ≥60 msec	
	N	n (%)	N	n (%)
1 h Post Dose				
2 h Post Dose				
4 h Post Dose				
72 h Post Dose				

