In tables of severity, maximum severity observed for the parameter after dosing will be summarized. Tables of maximum severity for “Any Parameter” will be included for chemistry, hematology, and urinalysis laboratory results. In these tables, the maximum severity across all laboratory results in the respective category is summarized by visit, and from maximum severity post baseline. Ordinarily, only the maximum severity event will be counted in the summary tables. For instance, if subject has a mild decrease and a moderate increase observed post-dose, they will be counted once as a moderate increase for maximum severity post-baseline. In the exceptional case that a subject has an increase and a decrease of equal maximum severity, they will be counted twice for maximum severity post baseline, once for an increase and once for a decrease.

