9.7. Vital Signs and Physical Evaluations

VS measurements include systolic blood pressure, diastolic blood pressure, pulse rate, respiratory rate, and oral temperature. VS will be assessed within 60 min of dosing (baseline), 1 h (± 10 min), 2 h (± 10 min), and 4 h (± 10 min) after dosing, and at Day 2, Day 3, Day 4, and Day 8 or ET. VS will be tabulated by parameter, severity grading, and visit (Table 96, Table 97, Table 98, Table 99, Table 100, and Table 101) and listed (Listing 15). Additionally, descriptive statistics, including mean, standard deviation, median, minimum and maximum will be presented to summarize VS at baseline and post-dose and will also present change from baseline (Table 102, Table 103, Table 104, Table 105 and Table 106). For each vital sign, individual line plots showing the vital sign over time will be shown by parameter (Figure 28, Figure 29, Figure 30, Figure 31 and Figure 32). Subjects will not be labeled in the line plots, as the purpose of the figures is to give an overall trend of trajectory.

In tables of severity, maximum severity observed for the parameter after dosing will be summarized. Tables of maximum severity for “Any Parameter” will be included for VS results. In these tables, the maximum severity across all VS is summarized by visit, and from maximum severity post baseline. Ordinarily, only the maximum severity event will be counted in the summary tables. For instance, if subject has a mild decrease and a moderate increase observed post-dose, they will be counted once as a moderate increase for maximum severity post-baseline. In the exceptional case that a subject has an increase and a decrease of equal maximum severity, they will be counted twice for maximum severity post baseline, once for an increase and once for a decrease.

A complete physical examination (PE), except genital, rectal and breast exams, will be conducted at Screening and at Day 8 (± 2) or ET. This examination will assess general appearance, HEENT (head, eyes, ears, nose and throat), heart, lungs, abdomen, skin, musculoskeletal system, and lymph nodes, and include an abbreviated neurological exam. An abbreviated PE will be performed on Day -1 (unless a complete PE was performed < 7 days before dosing) and Day 4. An abbreviated PE differs from a complete PE in that the

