Total protein decrease – g/dL	5.2 – 6.0	4.8 – 5.1	<4.8
Albumin decrease – g/dL	2.8 – 3.4	2.5 – 2.7	<2.5
AST increase – U/L	43 – 104	105 – 209	≥210
ALT increase, male – U/L	73 – 179	180 – 359	≥360
ALT increase, female – U/L	45 – 109	110 – 219	≥220
Alkaline phosphatase increase – U/L	151 – 240	241 – 360	>360
Total bilirubin (serum) increase – mg/dL (with other LFTs in the normal range)	1.4 – 2.0	2.1 – 2.5	>2.5
Total bilirubin (serum) increase – mg/dL (accompanied by a >3 x ULN increase in ALT or AST)**	1.4 – 1.6	1.7 – 2.0	>2.0
Hemoglobin decrease, female – g/dL	11.0 – 11.5	9.5 – 10.9	< 9.5
Hemoglobin decrease, male – g/dL	12.0 –13.5	10.0 – 11.9	<10.0
WBC increase – cell/mm ³	11,000 – 15,000	15,001 – 20,000	>20,000
WBC decrease – cell/mm ³	2,500 –3,500	1,500 – 2,499	<1,500
Neutrophils decrease – cell/mm ³	1,200 – 1,399	1,000 – 1,199	<1,000
Lymphocytes decrease – cell/mm ³	750 – 999	500 – 749	<500
Monocytes increase – cell/mm ³	1,101 – 2,000	2,001– 3000	>3,000
Eosinophils increase – cell/mm ³	500 – 750	751 – 1,500	>1,500
Basophils increase – cell/mm ³	201 – 500	501 – 800	>800
Platelets decrease – cell/mm ³	120,000 – 125,000	100,000 – <120,000	<100,000
Urine*			
Protein	1+	2+	>2+

Laboratory AEs	Mild (Grade 1)	Moderate (Grade 2)	Severe (Grade 3)
Glucose	1+	2+	>2+
Blood (dipstick)	1+	2+	>2+
Blood (microscopic) - RBCs per HPF	6-10	11-50	>50 and/or gross blood
WBC (microscopic) – WBC per HPF	5-10	11-50	>50
Bacteria (microscopic)	few	moderate	Many

* Institutional normal reference ranges and allowable ranges at screening are provided in Appendix B of the protocol.
 **ALT, males: >216 U/mL; ALT, females: >132 U/mL; AST, male or female: >126 U/mL)
Note 1: If a subject was accepted into the trial with a laboratory value of an analyte that overlaps with values used for grading Grade 1 (mild) laboratory abnormalities, an AE will be reported if the on-study value of the same analyte is different (worse) from the baseline.
Note 2: Safety laboratory results that are abnormal according to the local laboratory reference range, but not considered a Grade 1 abnormality, will be evaluated by the study site clinician and reported as Grade 1 abnormality if clinically significant. If not clinically significant, these will not be considered laboratory AEs and will thus not be graded, but will be recorded in the source document and followed-up clinically at the discretion of the study site clinician.

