Figure 19: Individual Laboratory Results by Scheduled Visits: Changes from Baseline – Hematocrit

This figure will repeat Figure 3 for Hematocrit.

Figure 20: Individual Laboratory Results by Scheduled Visits: Changes from Baseline – Erythrocytes

This figure will repeat Figure 3 for Erythrocytes.

Figure 21: Individual Laboratory Results by Scheduled Visits: Changes from Baseline – Leukocytes

This figure will repeat Figure 3 for Leukocytes.

Figure 22: Individual Laboratory Results by Scheduled Visits: Changes from Baseline – Neutrophils

This figure will repeat Figure 3 for Neutrophils.

Figure 23: Individual Laboratory Results by Scheduled Visits: Changes from Baseline – Lymphocytes

This figure will repeat Figure 3 for Lymphocytes.

Figure 24: Individual Laboratory Results by Scheduled Visits: Changes from Baseline – Monocytes

This figure will repeat Figure 3 for Monocytes.

Figure 25: Individual Laboratory Results by Scheduled Visits: Changes from Baseline – Eosinophils

This figure will repeat Figure 3 for Eosinophils.

Figure 26: Individual Laboratory Results by Scheduled Visits: Changes from Baseline – Basophils

This figure will repeat Figure 3 for Basophils.

Figure 27: Individual Laboratory Results by Scheduled Visits: Changes from Baseline – Platelets

This figure will repeat Figure 3 for Platelets.

Section 14.3.6 Displays of Vital Signs

Figure 28: Individual Vital Signs by Scheduled Visits: Systolic Blood Pressure

[figure not shown]

Figure 29: Individual Vital Signs by Scheduled Visits: Diastolic Blood Pressure

This figure will repeat Figure 28 for Diastolic Blood Pressure.

Figure 30: Individual Vital Signs by Scheduled Visits: Pulse Rate

This figure will repeat Figure 28 for Pulse Rate.

Figure 31: Individual Vital Signs by Scheduled Visits: Respiratory Rate

This figure will repeat Figure 28 for Respiratory Rate.

Figure 32: Individual Vital Signs by Scheduled Visits: Temperature

This figure will repeat Figure 28 for Temperature.

Figure 33: Individual ECG by Scheduled Visits: PR Interval, Aggregate

[figure not shown]

Figure 34: Individual ECG by Scheduled Visits: QRS Duration, Aggregate

This figure will repeat Figure 33 for Diastolic Blood Pressure.

Figure 35: Individual ECG by Scheduled Visits: QT Interval, Aggregate

This figure will repeat Figure 33 for Pulse Rate.

Figure 36: Individual ECG by Scheduled Visits: QTcF Interval, Aggregate

This figure will repeat Figure 33 for QTcF Interval, Aggregate.

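### SAP severity shells use the wrong templates: the leukocyte tables (62, 71) merge rises with falls, and the vital-sign tables (96–101) have no row for six of seven post-dose time points

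*SAP*

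**What the plan says.** **Templates.** In SAP Appendix 1, Table 19 has the columns None, Grade 1, Grade 2, Grade 3 and Missing. Table 20 splits each grade into Low and High. Tables 32 and 33 are the undirected and Low/High layouts for abnormal results related to treatment. All four have three rows: Baseline, Day 4 and Max Severity Post Baseline. The table note says that the last row covers every post-baseline reading, unscheduled ones included.

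**Leukocytes.** Table 62: "This table will repeat Table 19 for Leukocytes". Table 71: "This table will repeat Table 32 for Leukocytes". SAP Table 4 has one grading row for a white-cell increase and a second one, "WBC decrease – cell/mm" (cubed), for a fall. For a subject with an increase and a decrease of equal maximum grade, SAP 9.6 says "they will be counted twice for maximum severity post baseline, once for an increase and once for a decrease".

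**Vital signs.** SAP 9.7 says "VS will be tabulated by parameter, severity grading, and visit", citing Tables 96 to 101. It schedules post-dose readings at 1 h, 2 h and 4 h and on Days 2, 3, 4 and 8 (or early termination). Tables 96, 98, 100 and 101 copy Table 19. Tables 97 and 99 copy Table 20, for example "This table will repeat Table 20 for Vital Signs – Systolic Blood Pressure".

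**Smaller slips.** Table 29: "This table will repeat Table 20 for Alanine Aminotransferase", although Table 4 grades ALT for increase only. Under the QT-interval caption, the body of Figure 35 reads "This figure will repeat Figure 33 for Pulse Rate". The body of Figure 34, the QRS figure, names diastolic pressure.

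**The concern.** A programmer who builds the tables literally from these shells produces displays that do not match the SAP's own text.

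For leukocytes, a raised and a lowered count of the same grade fall in one cell, and the count alone does not say which occurred. The rule in SAP 9.6 presupposes that direction is visible. In an undirected table, counting a subject once for an increase and once for a decrease would enter that subject twice in the same cell.

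For vital signs, a template made for laboratory tests, which have one scheduled post-dose visit, is applied to measurements with seven. The severity-by-visit summary promised in 9.7 shrinks to one scheduled post-dose visit plus an overall maximum. Safety and tolerability is the trial's only secondary objective, and its safety review advises on using the 4-g dose in a thorough QT study, so these tables should show what the text says they show.

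**Working it through.** No test, power or event figure is involved. The check sets each shell against the grading scales (SAP Tables 3 and 4) and the visit schedule (SAP 9.7), and counts.

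**1. Which parameters are graded in both directions, and which layout do they get?** Only parameters with a severity table are considered.

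| Parameter | Graded both ways? | Layout |
|---|---|---|
| Sodium, potassium, bicarbonate, glucose | Yes (Table 4) | Low/High (Table 20; related results, Table 33) |
| Systolic pressure, pulse rate | Yes (Table 3) | Low/High (Table 20) |
| Leukocytes | Yes (Table 4) | Undirected (Table 19; related results, Table 32) |
| ALT | No, increase only | Low/High in Table 29; undirected in Table 42 (related) |

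The other graded hematology parameters run one way only. Hemoglobin, neutrophils, lymphocytes and platelets are graded for decrease; monocytes, eosinophils and basophils for increase. Leukocytes are therefore the only hematology parameter graded both ways, and the only two-way parameter in the whole set without Low/High columns.

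**2. What the leukocyte cells merge.** Per mm³:
- Increase: Grade 1 is 11,000–15,000, Grade 2 is 15,001–20,000, Grade 3 is above 20,000.
- Decrease: Grade 1 is 2,500–3,500, Grade 2 is 1,500–2,499, Grade 3 is below 1,500.

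That is 2 directions × 3 grades = 6 categories, shown in 3 columns. With a safety population of 8, one subject at Grade 1 high and another at Grade 1 low give 1 + 1 = 2, and 2/8 = 25%. The cell reads 2 (25%) Mild.

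**3. Vital-sign rows.**
- Scheduled post-dose time points in 9.7: 1 h, 2 h, 4 h, Day 2, Day 3, Day 4, Day 8 = 7.
- Time points with their own row in Tables 19 and 20: Day 4 = 1.
- Without a row: 7 − 1 = 6, in each of six tables.
- Rows needed: Baseline + 7 + Max Severity Post Baseline = 9, against 3 in the shells.

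Direction is handled correctly here. Systolic pressure and pulse rate have Low/High columns; diastolic pressure, respiratory rate and temperature are graded upward only.

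**4. Slip or intention?** The neighbouring shells suggest a slip. Table 102 (vital-sign summary statistics) has rows for all seven post-dose time points, and Table 108 (ECG severity) has 1 h, 2 h, 4 h and 72 h. The titles of Tables 96 to 101 themselves promise a breakdown by time point.

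**The case against.** The case on the other side is substantial, and most of it limits the consequences.

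- **The early vital-sign readings are not discarded.** A reader might infer that the 1 h, 2 h and 4 h readings drop out of the severity tables. They do not: a graded reading at 1 h counts in Max Severity Post Baseline. Only its time is lost.
- **Timing can be recovered elsewhere.** A reader might also infer that an early rise could not be told from a late isolated reading. Listing 15 gives each reading with visit, date, clock time, grade and change from baseline. Tables 102 to 106 summarise every scheduled time point, and Figures 28 to 32 plot individual courses, though without subject labels. With eight subjects the listing is quick to read.
- **Direction can be recovered too.** Table 17 and Listing 10 show each leukocyte result with its grade, Table 81 gives minimum, maximum and change, and Figure 21 plots individual courses.
- **The count-twice rule will rarely apply to leukocytes.** Only one post-dose laboratory visit is scheduled, so one subject could show both directions only through an unscheduled test. SAP 9.6 keeps such tests out of tabular summaries, although the table note includes them in the maximum row. Mixing of directions between subjects needs no such case.
- **Nearness to peak exposure is not established.** It is tempting to say that the missing rows are those closest to peak concentration. Protocol 2.1.2 says only that fasting absorption was fairly quick, and the T_max range is blacked out.
- **Low counts are not alone in overlapping or escaping the entry limits.** Protocol Appendix B accepts 3.5 to 11.5 ×10³/µL, so Grade 1 overlaps the entry range at both ends. The case for separate columns is that the directions mean different things, not that only one of them matters.
- **The text of 9.7 is right, and shells are mock-ups.** That is so, but the shells are what gets programmed. Where the two disagree, the SAP should be corrected, not left to the programmer.

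What stands is that the tables as specified do not separate direction for leukocytes and do not deliver the by-visit severity display for vital signs.

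**Conclusion.** The point holds as a specification error in descriptive secondary safety displays. Two leukocyte tables (62 and 71) cannot separate a rise from a fall. Six vital-sign tables (96 to 101) lack a row for 6 of 7 post-dose time points, so the timing of graded abnormalities is lost within those tables, though not from the report as a whole.

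The 25% illustration assumes 8 dosed subjects. If replacements bring the safety population to 10, the same two subjects give 2/10 = 20%. The finding also assumes that the shells will be programmed as written.

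The secondary endpoint for vital signs is change from baseline, which Tables 102 to 106 deliver in full. No PK parameter or PK summary is touched. The ALT layout and the body text of Figures 34 and 35 are clerical: the unused Low columns in Table 29 lose no information, and the figure captions, the figure list and SAP 9.9 all name QRS and QT correctly. The template errors should be corrected because the remedy is exact and costs almost nothing.

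**What to change.** Edit SAP Appendices 1 and 2 as follows.

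- **Table 62:** base it on Table 20 in place of Table 19.
- **Table 71:** base it on Table 33 in place of Table 32.
- **Tables 96 to 101:** use the rows Baseline, 1 h, 2 h, 4 h, Day 2, Day 3, Day 4, Day 8 and Max Severity Post Baseline. Keep the Low/High columns in Tables 97 and 99 and the undirected columns in Tables 96, 98, 100 and 101.
- **Clerical:** base Table 29 (ALT) on Table 19. Correct the body text of Figure 34 to QRS duration and of Figure 35 to QT interval.

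The cost is a set of shell edits, best made before final data lock. No new data, visits or analyses are needed, and the method text in SAP 9.6 and 9.7 can stay as it is for this point.
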